3.5 Objectives and hypotheses of the clinical investigation

Main objective

The primary objective of this research is to assess the effectiveness of MEL-T01 in reducing MDD symptoms. The subjects are randomised into three research arms (MEL-T01, MEL-S01, and TAU), and their subject health questionnaire (PHQ-9) scores are measured on five occasions (see Table 1).

Research arms

- MEL-T01
- MEL-S01
- TAU

Time intervals

- T0, before subjects in MEL-T01 and MEL-S01 arm begin the active intervention.
- T1, 4 weeks after T0
- T2, 8 weeks after T0

- T3, 12 weeks after T0
- T4, 24 weeks after T0

Primary hypotheses

- MEL-T01 is superior to TAU in alleviating MDD symptoms as measured by the change in subject health questionnaire (PHQ-9) score between time points T0 (before the intervention) and T3 (after a 12-week intervention).
- MEL-S01 is superior to TAU in alleviating MDD symptoms as measured by the change in PHQ-9 score between T0 and T3.
- MEL-T01 superior to MEL-S01 as measured by the change in PHQ-9 score between T0 and T3.

Secondary hypotheses

- In terms of a score change from T0 to T3,
MEL-T01 is superior to TAU,
and MEL-S01 is superior to TAU,
and MEL-T01 superior to MEL-S01 in:
 - reducing depression symptoms as measured by quick inventory of depressive symptomatology (QIDS),
 - reducing rumination as measured by short-version ruminative response scale (RRS),
 - reducing anxiety symptoms as measured by general anxiety disorder (GAD-7),
 - reducing the disability symptoms as measured by sheehan disability scale (SDS),
 - increasing positive emotions as measured by positive valence systems scale (PVSS),
 - and
 - improving well-being as measured by the WHO-five well-being index (WHO-5)
- The effect of the MEL-T01 is mediated by the training dose, as measured by the subject's total game-playing time during the intervention, and evidenced by a positive correlation between MEL-T01 game time and reduction in symptoms as measured by the PHQ-9.
- The effect of the MEL-S01 is mediated by the training dose, as measured by the subject's total game-playing time during the intervention, and evidenced by a positive correlation between MEL-S01 game time and reduction in symptoms as measured by the PHQ-9.

- The effects of MEL-T01 on depressive symptoms as measured by PHQ-9 are mediated by positive game experience as measured by the immersive experiences questionnaire (IEQ).

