3.7.3 Hypothesis tests and multiple comparisons

Primary and secondary objectives in this clinical study are to demonstrate a statistical difference on outcome measure mean change scores between the following groups:

1. MEL-T01 and MEL-S01
2. MEL-T01 and TAU
3. MEL-S01 and TAU

We will first assess whether we use a parametric or non-parametric test.

- Using the Shapiro-Wilk test we explore if MEL-T01, MEL-S01, and TAU model residuals are normally distributed regarding PHQ-9.
- Using Levene's test we test whether the variance of MEL-T01, MEL-S01 and TAU model residuals are equal regarding PHQ-9.
- If both tests are $p > 0.05$, we will use a repeated measures Linear Mixed Model; If either test is $p < 0.05$, we will use a repeated measures Linear Mixed Model with robust standard errors.
- For primary endpoint evaluation (PHQ-9), we will conduct a one-tailed test for the arm pairs MEL-T01-vs.-MEL-S01, MEL-T01-vs.-TAU, and MEL-S01-vs.-TAU. We

are using a significance level of 0.05. Using Holm-Bonferroni correction, we find the multiple-comparison corrected $p = 0.05/3 = 0.0167$.

Change scores are defined as the scores obtained between the pre-intervention (T0) assessment and the during/post-intervention assessments. The general formulation of the null and alternative hypotheses are

$$H_0: \mu_x = \mu_y$$

$$H_1: \mu_x \neq \mu_y$$

where H_0 is the null hypothesis, H_1 is the alternative hypothesis and $x, y \in \{A, B, TAU\}$, $x \neq y$.

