3.7.4 Power and sample size

3.7.4.1 Power analysis

A power analysis was conducted to determine appropriate sample size for the study to detect a statistical difference between change scores for the primary hypothesis in a two tailed, repeated measures t-test. Assuming that our samples are independent and identically distributed with normal distribution (see [3.7.3](#)), we analyse the required sample size as follows:

- We conduct sample size analysis using G*Power 3.1.9.7
- We use a two-tailed t-test.
- Cohen (1988) suggests a small effect size is 0.20 and medium effect size is 0.50. As a point of comparison, a meta-analysis of internet-based treatments for adult depression have reached an average effect size of 0.41 (Anderson & Cuijpers, 2009). Meanwhile, Motter et al. (2016) found in their meta-analysis that computerised cognitive training had an effect size of 0.43 on depression symptom severity. Thus, we use an effect size $d = 0.40$.
- We use an alpha error probability of 0.0167 that corresponds to an alpha level of 0.05 with Bonferroni correction for the three primary endpoint tests.
- We use power of 0.80
- We allocate subjects equally to the three arms, leading to allocation ratio of 1:1:1

This leads to a total sample size of 133 per arm and with three arms this equals 399 subjects, which we round to **400 subjects** that we aim to have in T3.

Karyotaki et al. (2015) explored the dropout in self-guided web-based interventions for depression using different psychotherapeutic approaches. While their approach is based on psychotherapies, and ours on cognitive training, the medium of training is the same

(web-based), the intervention is self-guided, and they target people with depression. Karyotaki et al. found that in 10 RCTs 59% of the subjects dropped out before completing half the treatment modules.

Meanwhile, Torous et al. (2020) explored dropout rates for app interventions for depression. Considering publication bias, they found a dropout rate of 47.8%.

Considering the above, we assume a dropout rate of 50%. Thus, we aim to recruit up to 400 subjects / 0.50 = 800 subjects to begin the study.

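### The primary tests are one-tailed at 0.0167 but the sample size is two-tailed at 0.0167, so the threshold per direction is twice the one the sizing used; the plan should state one sidedness, one family level and the Holm steps

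*Combined protocol and SAP*

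**What the plan says.** - **Test (3.7.3).** "For primary endpoint evaluation (PHQ-9), we will conduct a one-tailed test for the arm pairs" formed by MEL-T01, MEL-S01 and TAU. The investigators "are using a significance level of 0.05", without saying whether it is one-sided or two-sided.
- **Multiplicity (3.7.3).** "Using Holm-Bonferroni correction, we find the multiple-comparison corrected" value of 0.05/3 = 0.0167. No further cut is given.
- **Formal hypotheses (3.7.3).** The null is equal means and the alternative is unequal means, so the alternative is two-sided.
- **Worded hypotheses (3.5, repeated in the synopsis, 3.1.6).** All three primary hypotheses are directional, for example "MEL-T01 is superior to TAU in alleviating MDD symptoms as measured by the change in subject health questionnaire (PHQ-9) score".
- **Sample size (3.7.4.1).** "We use a two-tailed t-test". "We use an alpha error probability of 0.0167 that corresponds to an alpha level of 0.05 with Bonferroni correction". "We use power of 0.80". With d = 0.40 and equal allocation this gives 133 per arm.
- **Interim rules (3.7.5.1 and 3.7.5.2).** One-tailed 0.025 for benefit, and one-tailed 0.0125 for each of two harm tests.

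**The concern.** Sidedness, family level and multiplicity procedure together form the decision rule for the primary hypotheses. Here 3.7.3 and 3.7.4.1 use the same number, 0.0167, for two different rules, and nothing says which governs. Two things follow. First, some results would count as superiority under the analysis section but not under the rule that fixed the sample size. Second, the stated power does not describe the planned test. If this is still open when the data are unblinded, choosing between the two readings becomes a choice made with the results in view.

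**Working it through.** **Inputs.** From 3.7.4.1: d = 0.40 (so SD = 1), alpha 0.0167, power 0.80, 1:1:1 allocation, 133 per arm, 50% dropout. From 3.7.3: one-tailed tests, level 0.05, cut 0.05/3.

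**1. Reproduce the stated sample size.** Normal approximation, two-tailed: n = 2(z₁₋α/₂ + z₁₋β)²/d² = 2(2.393 + 0.842)²/0.16 = 130.8, so 131. The noncentral t calculation gives 133, with power 0.803. Then 3 × 133 = 399, rounded to 400, and 400/0.50 = 800. The plan's figures reproduce, and they rest on the two-tailed test.

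**2. The same calculation for the test in 3.7.3.** One-tailed: n = 2(2.127 + 0.842)²/0.16 = 110.2, so 111; noncentral t gives 112. At 133 per arm the noncentrality is 0.40 × √(133/2) = 3.262. Normal-approximation power is Φ(3.262 − 2.127) = 0.872 one-tailed and Φ(3.262 − 2.393) = 0.807 two-tailed.

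| Rule | Threshold in the superiority direction | z cut | n per arm for 0.80 (noncentral t) | Power at 133 (noncentral t) |
|---|---|---|---|---|
| 3.7.4.1: two-tailed 0.0167 | 0.0083 | 2.39 | 133 | 0.803 |
| 3.7.3: one-tailed 0.0167 | 0.0167 | 2.13 | 112 | 0.869 |
| One-tailed 0.025/3 | 0.0083 | 2.39 | 133 | 0.802 |

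**3. Results that change verdict.** A favourable result with one-tailed p below 0.0167 has two-sided p below 2 × 0.0167 = 0.033. The sizing rule requires two-sided p below 0.0167. At the first cut the two sections therefore disagree for favourable results with two-sided p between 0.0167 and 0.033.

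**4. Family-wise error.** Three one-tailed tests at 0.05/3 cannot exceed 3 × 0.0167 = 0.05. A simulation of the three correlated pairwise z-tests under the global null (1,000,000 replicates) gives 4.5%. Two-tailed tests at 0.05/3 give 4.4%, counting both directions.

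**5. Comparison with the interim rules.** The benefit test is one-tailed at 0.025, and 0.0125 = 0.025/2 for the harm tests. Where the interim section tests one-tailed, it works from 0.025. Section 3.7.3 works from 0.05.

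**6. Holm against 0.0167 for every test.** Holm compares the ordered p-values with 0.05/3 = 0.0167, 0.05/2 = 0.025 and 0.05. With a smallest p below 0.0167, a second p of 0.02 passes Holm and fails a flat cut. Simulated power for each contrast with d = 0.40, at 133 per arm:

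| Assumed effects (T01–TAU / T01–S01 / S01–TAU) | One-tailed, flat 0.0167 | One-tailed Holm, family 0.05 | Two-tailed, flat 0.0167 | Two-tailed Holm, family 0.05 |
|---|---|---|---|---|
| 0.40 / 0.40 / 0 | 0.87 | 0.90 | 0.81 | 0.835 |
| 0.80 / 0.40 / 0.40 | 0.87 | 0.95 | 0.81 | 0.90 |

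The documents give neither pattern; they state only d = 0.40. The two rows show how far the Holm gain depends on the truth.

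**The case against.** The strongest defence is that the plan is directional where it matters. The worded primary hypotheses and the interim tests are one-sided, so one-tailed testing is the prevailing choice, and the symbolic H1 and the sizing are the outliers. Sizing two-tailed and analysing one-tailed is conservative. The cut 0.05/3 is Holm's correct first step, and naming the procedure is arguably enough. All of this stands as far as it goes, and it rules out three stronger readings.

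- **A reader might infer that type I error is inflated.** The documents do not support this. Directional family-wise error is about 4.5%, within the stated 0.05. A rate of about 8.4% arises only for two-sided tests at 0.033 each, which counts wrong-direction rejections that the planned tests cannot make.
- **A reader might infer that the trial is underpowered.** The discrepancy runs the other way: 0.87 against a stated 0.80.
- **A reader might infer that Holm has been replaced by a flat cut.** The text does not say that 0.0167 applies to every ordered p-value. If it were applied that way, power would be lost but error would not be inflated.

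The defence does not settle which rule governs. It leaves unsaid whether 0.05 is one-sided, and it does not explain why the final analysis allows twice the per-direction threshold used in the sizing.

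**Conclusion.** The inconsistency is real and lies in the decision rule for all three primary hypotheses. Its size is a factor of two in the per-direction threshold (0.0167 against 0.0083). That gives a band of favourable results, two-sided p from 0.0167 to 0.033, whose verdict depends on the section followed. It also gives a stated power (0.80) that belongs to a different test from the one planned (about 0.87). The point is a need for alignment, not evidence of excess false positives or too few subjects. Incomplete Holm wording is a secondary part of it, since 3.7.4.1 says Bonferroni and the later steps appear nowhere.

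The power figures assume a two-sample t-test with d = 0.40 and 133 evaluable subjects per arm, as in 3.7.4.1. The planned analysis is a mixed model, so they carry over only approximately. The error rates take no account of the interim look.

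**What to change.** In 3.7.3, specify one of two equivalent rules:

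- two-tailed tests at family-wise 0.05, H1 kept as written, with Holm's ordered p-values compared with 0.0167, 0.025 and 0.05; or
- one-tailed tests at family-wise 0.025, H1 rewritten to match the directional hypotheses in 3.5, with ordered p-values compared with 0.0083, 0.0125 and 0.025.

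Use the same sidedness and the same name for the correction in 3.7.4.1. Settle this before the primary comparison is unblinded.

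**Cost.** A few sentences, no new subjects, and 133 per arm at power 0.80 under either rule. The price is the one-tailed power that the sizing did not count: about 0.87 falls to 0.81 per contrast at the first cut. Holm brings this back to about 0.835 if MEL-S01 equals TAU, or about 0.90 if effects are additive; both are assumed patterns. If the one-tailed plan would have run Holm in full, the like-for-like loss is about 0.90 to 0.835 in the first pattern and 0.95 to 0.90 in the second.

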3.7.5.1 Criteria for “clearly beneficial”

We will consider MEL-T01 to be clearly beneficial if it reaches the primary endpoint so that:

The reduction in PHQ-9 score from T0 to T3 is

greater for MEL-T01 than for TAU

AND

greater for MEL-T01 than for MEL-S01.

If both superiority conditions are met in a one-tailed t-test (or in a one-tailed Wilcoxon test if the conditions defined in [3.7.3](#) for using a parametric test are not met) with an alpha-level of 0.025, the recruitment will be carried on until the next 33 data-analysis-qualified subjects have

been recruited to each of the three arms. After this recruitment goal has been achieved, the investigation will be terminated with the same process that is defined for the main termination condition (defined in [3.7.4.2](#)).

Thus, if evidence for MEL-T01 being clearly beneficial is observed, we will acquire a replication cohort to corroborate this observation and terminate the study.

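### The three primary contrasts are logically linked, and adding one step to Holm in section 3.7.3 would use that link to gain power for MEL-T01 versus MEL-S01 at no cost in patients or family-wise error

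*Combined protocol and SAP*

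**What the plan says.** Below, T01 and S01 stand for MEL-T01 and MEL-S01.

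- **Analysis (3.7.3).** For the primary endpoint, "we will conduct a one-tailed test for the arm pairs" T01–S01, T01–TAU and S01–TAU. The investigators "are using a significance level of 0.05". The section continues: "Using Holm-Bonferroni correction, we find the multiple-comparison corrected" value, printed as 0.05/3 = 0.0167. No second or third Holm threshold is printed, and no testing order is given.
- **Sample size (3.7.4.1).** "We use an alpha error probability of 0.0167 that corresponds to an alpha level of 0.05 with Bonferroni correction" for the three primary tests. With d = 0.40, power 0.80 and two tails ("We use a two-tailed t-test"), this gives 133 analysable subjects per arm.
- **Objectives (3.5).** "The primary objective of this research is to assess the effectiveness of MEL-T01 in reducing MDD symptoms". The three contrasts are then listed as primary hypotheses without rank.
- **Interim (3.7.5.1).** "We will consider MEL-T01 to be clearly beneficial if it reaches the primary endpoint so that" T01 beats both TAU and S01. The two conditions are joined by AND, and neither is placed before the other.

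**The concern.** The multiplicity rule treats the three contrasts as if any combination of them could be null, but three pairwise comparisons among three arms constrain each other. Bonferroni ignores the constraint, and so does a correctly run Holm, so both are stricter than they need to be once T01–TAU has been won.

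The contrast most affected is T01–S01. Section 3.6.2 rests the claim about the mechanistic role of cognitive training on the comparator. Section 3.2.12.2 expects both games to have positive effects, so the T01–S01 difference may well be smaller than T01–TAU. That is the setting, among those examined, where the unused alpha is worth most.

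The printed threshold adds an ambiguity. A reader could apply 0.0167 to all three tests, although the named procedure does not require it.

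**Working it through.** **Inputs.** Family alpha 0.05 (3.7.3); d = 0.40, 1:1:1 allocation and 133 per arm (3.7.4.1). The documents give one d for all contrasts. Any other effect below is an assumption, in SD units.

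**1. Reproduce the plan's figure.** The noncentrality is d × √(n/2) = 0.40 × √(133/2) = 3.26. With 264 degrees of freedom and two-sided alpha 0.0167, the critical t is about 2.41. Power is about Φ(3.26 − 2.41) = Φ(0.85) = 0.80. The exact noncentral t gives 80.3%, and the required n is 132.2, rounded up to 133. The plan's figure is confirmed.

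**2. Power of a single T01–S01 test at d = 0.40, by threshold (noncentral t).**

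| Alpha | Two-sided | One-sided |
|---|---|---|
| 0.0167 | 80.3% | 86.9% |
| 0.025 | 84.3% | 90.1% |
| 0.05 | 90.1% | 94.6% |

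**3. The rule examined.** Run Holm (ordered p-values against 0.0167, 0.025 and 0.05). If Holm rejects T01–TAU, test T01–S01 and S01–TAU each at 0.05.

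**4. Why family-wise error is controlled.**
- *The T01–TAU null is true.* The rule departs from Holm only after Holm has rejected that null, which is already a false rejection. The event of at least one error is the same as under Holm, with probability at most 0.05.
- *The T01–TAU null is false.* The other two nulls cannot both be true. One-sided: T01 ≤ S01 and S01 ≤ TAU together imply T01 ≤ TAU. Two-sided: T01 = S01 and S01 = TAU together imply T01 = TAU. At most one true null remains, and it is never tested above 0.05.

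Every Holm rejection is kept, so the rule never rejects less than Holm. With one-sided nulls the extra step is valid only from T01–TAU: rejecting either of the other two leaves the remaining pair free to be both null. Simulated family-wise error peaked at 0.0502 (1,000,000 runs per setting) and 0.0506 (a separate check, 400,000 runs), which is 0.05 within simulation error.

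**5. Where the gain arises.** T01–S01 gains over Holm exactly when T01–TAU is rejected first, both remaining p-values exceed 0.025, and the T01–S01 p-value is at most 0.05. Holm then stops at its second step. If S01 clearly beats TAU, Holm usually reaches 0.05 for T01–S01 anyway, so little is gained.

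**6. Power for T01–S01 at 133 per arm** (simulated correlated contrasts, 300,000 runs, equal variances, no interim look).

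| T01–TAU / S01–TAU / T01–S01 | Tails | Flat 0.0167 | Holm | Holm + step | Gain over Holm |
|---|---|---|---|---|---|
| 0.40 / 0 / 0.40 | two | 80.6% | 83.5% | 87.0% | 3.5 |
| 0.40 / 0 / 0.40 | one | 87.2% | 89.8% | 92.4% | 2.6 |
| 0.40 / 0.20 / 0.20 (assumed) | two | 22.2% | 28.3% | 35.7% | 7.4 |
| 0.40 / 0.20 / 0.20 (assumed) | one | 30.9% | 40.6% | 48.0% | 7.4 |
| 0.80 / 0.40 / 0.40 (assumed) | two | 80.7% | 90.1% | 90.3% | 0.2 |
| 0.80 / 0.40 / 0.40 (assumed) | one | 87.1% | 94.6% | 94.7% | 0.1 |

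In the first setting, two-sided power to win both T01–TAU and T01–S01 is about 70%, 75% and 79% under the three rules.

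**The case against.** **The plan names a valid procedure.** Holm controls the error rate and is already stepwise, so choosing a sharper rule is optimisation. This stands. A reader might infer from the printed 0.0167 that T01–S01 is always judged at one third of alpha. The documents do not support that: under the named Holm procedure, 0.0167 applies only to the smallest p-value. The fair comparison is with Holm, where the gain is 0.1 to 7.4 points in the table, rather than the larger gap from flat Bonferroni.

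**The sample size already pays for the split.** This stands too. A reader might conclude that the correction leaves T01–S01 underpowered. At the plan's own d = 0.40 it does not: power is 80.3% two-sided or 86.9% one-sided at 0.0167. At an assumed 0.20, power stays below half even with the extra step, so the effect size is the limit there.

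**T01–TAU as a fixed gate.** A reader might take the interim definition as making T01–TAU the natural first test. That definition is symmetric, and section 3.5 ranks no contrast. A fixed gate also has a real cost: with T01–TAU at 0.2 and T01–S01 at 0.4, two-sided power for T01–S01 is about 36%, against 81% under Holm. It is not recommended.

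**Error control is claimed too broadly.** Partly stands. The guarantee covers the final-analysis family only. Section 3.7.5.1 adds an efficacy look at one-tailed 0.025 with no stated adjustment of the final threshold. Sidedness is also unsettled: 3.7.3 has one-tailed tests with a two-sided alternative, and 3.7.4.1 is two-tailed.

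**Conclusion.** The point holds as a free improvement together with a needed clarification. Section 3.7.3 names Holm but prints only the Bonferroni threshold, and neither rule uses the link between the contrasts. Holm plus a full-alpha step after a T01–TAU rejection keeps family-wise error at or below 0.05 in the final analysis, one- or two-sided, and never rejects less than Holm.

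The gain for T01–S01 over Holm is about 3 points when T01 is 0.40 better than both other arms. It is about 7 points if T01–S01 is only 0.20 and T01–TAU is 0.40, and close to zero when S01 is itself clearly effective. These figures assume 133 analysable subjects per arm, equal variances and no interim look; the effects per contrast other than d = 0.40 are assumptions. The documents do not support calling this an error that invalidates the plan or leaves the trial short of its stated power.

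**What to change.** In 3.7.3, replace the single threshold with a rule such as:

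> The three primary p-values are ordered and compared with alpha/3, alpha/2 and alpha by Holm's procedure, stopping at the first non-rejection. If MEL-T01 versus TAU is rejected, MEL-T01 versus MEL-S01 and MEL-S01 versus TAU are then each tested at the full family alpha.

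This costs two sentences. It needs no further subjects or data, and 133 per arm can stay, since sizing on 0.0167 remains conservative. The change should be dated and fixed before unblinded results are seen.

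Two matters need their own correction before the family alpha in this text has a definite meaning: one choice of sidedness across 3.7.3 and 3.7.4.1, and a stated treatment of the interim efficacy look in 3.7.5.1.

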3.6.3.7 Representativeness of investigation population in relation to target population

Our target population are people who suffer from MDD. We believe that through our recruitment process, we are able to reach a relevant population sample. Through HUS and VSSHP psychiatry we are able to recruit subjects who have more severe MDD symptoms. Through online recruitment we are able to reach subjects who have lesser MDD symptom severity.

We also gather demographic information with background questionnaires through which we can analyse the representativeness of the sample gathered and compare it in demographic terms of age, gender and education to see how well it represents the population (see 3.7.1.1.).

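### Section 3.7.3 names no baseline adjustment for the PHQ-9 change-score contrast, so precision may be lost, and its rule for failed assumptions conflicts with the interim rule in 3.7.5

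*Combined protocol and SAP*

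**What the plan says.** The target in protocol section 3.7.3 is a difference in mean change: "Primary and secondary objectives in this clinical study are to demonstrate a statistical difference on outcome measure mean change scores". Change is then defined: "Change scores are defined as the scores obtained between the pre-intervention (T0) assessment and the during/post-intervention assessments". The primary hypotheses in 3.5 fix the interval, for example "MEL-T01 superior to MEL-S01 as measured by the change in PHQ-9 score between T0 and T3", and 3.7.2 also ties the primary evaluation to T0 and T3.

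The model is identified by type only. Section 3.7.3 lists no fixed effects, covariance structure, baseline covariate or constraint on the T0 means, and no other section supplies them. The T0 score is available: 3.7.1.2 requires the T0 questionnaires before randomisation, and 3.7.2 requires a complete T0 PHQ-9 for every analysed subject.

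Two pre-tests choose the standard error: "Using the Shapiro-Wilk test we explore if MEL-T01, MEL-S01, and TAU model residuals are normally distributed regarding PHQ-9" and "Using Levene's test we test whether the variance of MEL-T01, MEL-S01 and TAU model residuals are equal regarding PHQ-9". Then: "If both tests are $p > 0.05$, we will use a repeated measures Linear Mixed Model". If either p-value is below 0.05, the same model is used with robust standard errors.

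The interim rules in 3.7.5.1 (benefit) and 3.7.5.2 (harm) use a one-tailed t-test. They switch to a rank test, "in a one-tailed Wilcoxon test if the conditions defined in" section 3.7.3, when those conditions fail.

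**The concern.** There are two separate problems.

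**Precision.** With complete data and free arm-by-visit means, a repeated-measures mixed model returns the plain difference in mean change. That contrast subtracts T0 with a coefficient fixed at 1 and does not let the data estimate the slope. Unless that slope happens to be 1, the contrast is noisier than a baseline-adjusted one. Section 3.7.4.1 plans for 50% dropout to keep 133 per arm, so precision that needs no extra subjects is worth having.

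**Conflicting rules.** Section 3.7.3 opens by announcing a choice between a parametric and a non-parametric test, but both of its branches are the same mixed model with different standard errors. Section 3.7.5 relies on a non-parametric branch that 3.7.3 does not contain. The same failed assumption therefore leads to a rank test at the interim and a mean difference at the end. A rank test does not test the mean change named in the hypotheses. Section 3.7.5 says the interim is to be programmed in advance, so the conflict has to be settled before it is run.

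**Working it through.** **1. The plan's own figure.** Inputs from 3.7.4.1: d = 0.40 on change scores, alpha 0.0167 two-tailed, power 0.80, equal allocation. A two-independent-sample t-test (noncentral t) gives 133 per arm with power 80.3%, as stated. The normal approximation, 2(2.394 + 0.842)²/0.40², gives 131. Under the one-tailed test of 3.7.3 at 0.0167, power at 133 per arm is 86.9%.

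**2. Variance ratio.** Let s0 and s3 be the within-arm SDs at T0 and T3, and r their correlation.

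- Change score: s0² + s3² − 2·r·s0·s3
- Baseline-adjusted: s3²(1 − r²)
- Ratio: R = s3²(1 − r²)/(s0² + s3² − 2·r·s0·s3), which is (1 + r)/2 when s0 = s3

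The first variance minus the second is (s0 − r·s3)², which is never negative. In large samples adjustment therefore loses nothing, and the gain is zero exactly when r·s3/s0 = 1.

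**3. Numbers.** The documents give neither r nor the SDs, so every row is an assumption. The standardised effect becomes 0.40/√R; for example, R = 0.75 gives 0.40/0.866 = 0.462.

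| SD(T3)/SD(T0) | r | R | n per arm for 80% (two-sided) | Power at 133, two-sided | Power at 133, one-sided |
|---|---|---|---|---|---|
| No adjustment | – | 1 | 133 | 80.3% | 86.9% |
| 1.0 | 0.3 | 0.650 | 87 | 94.9% | 97.1% |
| 1.0 | 0.5 | 0.750 | 100 | 91.2% | 94.8% |
| 1.0 | 0.7 | 0.850 | 113 | 87.0% | 91.9% |
| 1.25 | 0.3 | 0.784 | 105 | 89.8% | 93.8% |
| 1.25 | 0.5 | 0.893 | 119 | 85.1% | 90.5% |
| 1.25 | 0.7 | 0.981 | 130 | 81.1% | 87.5% |
| 1.25 | 0.8 | 1.000 | 133 | 80.3% | 86.9% |
| 1.5 | 0.5 | 0.964 | 128 | 81.9% | 88.1% |

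Check of one row (SD ratio 1.25, r = 0.5): 1.5625 × 0.75/(1 + 1.5625 − 1.25) = 1.1719/1.3125 = 0.893.

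**4. Simulation.** Three arms, 133 per arm, 6,000 runs per scenario, one-sided 0.0167. At r = 0.5 with equal SDs, power was 0.876 for change scores with the pre-tested standard error and 0.946 for baseline adjustment with robust errors. The standard-error ratio was 0.867, against √0.75 = 0.866.

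**5. What the pre-tests do.** Over six null scenarios, type I error was 0.0165 to 0.0218 by the pre-test route and 0.0155 to 0.0180 by the adjusted robust route (nominal 0.0167, Monte Carlo SE about 0.0017). With both assumptions true, the pre-tests still switched the standard error in about 10% of trials, as expected from two 5% tests (1 − 0.95² = 0.0975).

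**6. The two rules side by side.**

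| Conditions in 3.7.3 | Final analysis (3.7.3) | Interim (3.7.5.1, 3.7.5.2) |
|---|---|---|
| Met | Mixed model, model-based errors | t-test |
| Not met | Mixed model, robust errors | Wilcoxon test |

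This conflict depends on no assumption about the data.

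**The case against.** The strongest reply is that the absence of adjustment is read from silence. A mixed model with T0 as a covariate, or with T0 means constrained equal, would already capture the gain, and 3.7.3 rules out neither. That stands. The claim is that the model is under-specified, with a loss if the unadjusted form is used.

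The gain is also uncertain. Requiring current MDD at entry may narrow the T0 spread relative to T3, which is the unfavourable direction in the table. That stands too, so the equal-SD figures should not be quoted alone.

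A reader might infer more than the documents support:

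- **That the normality test nearly always rejects.** This is true of raw bounded scores, but 3.7.3 tests model residuals. With assumed rounded 0–27 scores (T0 mean 15, SD 4.5; T3 mean 10, SD 5.5), raw scores rejected in 100% of runs at n = 399. Arm-centred change-score residuals rejected in only about 10% to 20%.
- **That robust errors add precision, or that the pre-tests seriously distort type I error.** The precision comes from the baseline covariate, and the type I effect was small. Dropping the pre-tests removes a data-dependent choice.
- **That recruitment source should be a covariate.** Section 3.6.3.7 links source to severity ("Through HUS and VSSHP psychiatry we are able to recruit subjects who have more severe MDD symptoms"), but the sign-up data listed in 3.7.1.1 do not name it as recorded.
- **That the primary contrast is spread over T1 to T3.** The wording about assessments during the intervention is a general definition; 3.5 and 3.7.2 fix T0 to T3.
- **That the point depends on low power for MEL-T01 against MEL-S01.** Section 3.7.4.1 plans d = 0.40 for all three contrasts, and the figures here use the same value.

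**Conclusion.** The point holds in two parts.

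First, 3.7.3 leaves baseline adjustment unstated. If the analysis is the plain change-score contrast, two-sided power of 80% at 133 per arm could be 87% to 95% with equal SDs (r from 0.7 down to 0.3). At an SD ratio of 1.25 it could be 81% to 90% over the same r, with nothing gained at r = 0.8. On the planned one-tailed test, power starts at 87%. These figures rest on assumed r and SDs and on the plan's d = 0.40. The direction does not: in large samples adjustment cannot lose precision.

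Second, the interim and final rules for failed assumptions contradict each other whatever the data look like.

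There is one limit. The analysis set is selected after randomisation by 24 hours of play (3.7.2). Baseline adjustment does not cure that selection. If the selected arms differ at T0, the adjusted and change-score contrasts can differ. The sponsor should make the change, but the design does not fail without it.

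**What to change.** - In 3.7.3, state that the primary estimate is the arm difference in PHQ-9 at T3 from one mixed model. The model should have either T0 PHQ-9 as a covariate with a visit-specific effect, or T0 means constrained equal across arms. List the fixed effects and covariance structure.
- Use robust standard errors always and delete the Shapiro-Wilk and Levene branch.
- In 3.7.5.1 and 3.7.5.2, replace the t-test/Wilcoxon pair with the same model, using a small-sample correction because the interim can be run with 33 per arm. This changes the test only; the criteria and thresholds are left as they are.
- Reconcile the model with 3.7.2, which substitutes the T2 score or the first score after cessation of use. State whether a substituted value enters as T3, or whether the model uses each score at its own visit and treats T3 as missing.
- Add recruitment source only if it is confirmed as recorded before randomisation.
- Report the unadjusted change-score contrast as a sensitivity analysis, with T0 means by arm in the analysed set, so that any divergence caused by selection is visible.

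The cost is an amendment to the wording and reprogramming of the interim. No new PHQ-9 data are needed. The work that takes thought is reconciling the model with 3.7.2.
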